^a Changed from E to S as a minimum of 3 evaluable participants are needed to make a dose-escalation decision.

^b Changed from D to S as a minimum of 3 evaluable participants are needed to make a dose de-escalation decision.

Note: E = escalate to the next higher dose level, S = stay at the current dose level, D = de-escalate to the next lower dose level; DU = de-escalate to the previous lower dose and the current dose will never be used again due to unacceptable toxicity.

Abbreviations: D = de-escalation; DLT = dose-limiting toxicity; DU = dose unsafe; E = escalation; mTPI-2 = modified toxicity probability interval; S = stay.

A dose level will be considered as having unacceptable toxicity, with no additional participants enrolled at that dose level and above, if it has an estimated 95% or more probability of exceeding the 30% target DLT rate. Otherwise, dose escalation is terminated when the prespecified maximum target dose is reached (AZD4573 12 mg).

If a stay decision is made, additional participants may be enrolled (usually in cohorts of 2 to 6 participants) up to a maximum of 9 total evaluable participants for a given dose level and a maximum of 24 evaluable participants for dose setting (ie, a maximum of 9 evaluable participants at each of two dose levels and 6 evaluable participants at the third dose level).

At any timepoint during the study, the occurrence of a fatal AE deemed related to study therapy (after full etiological work-up and in discussion with the SRC) will result in accrual stoppage and a comprehensive review of safety. In addition, potential safety signals arising from Grade ≤ 4 treatment-related AEs will be reviewed in the context of the overall benefit/risk. On review any event deemed to adversely affect overall benefit risk will trigger an ad hoc SRC for comprehensive safety review.

In the case of PHL, if bilirubin remains elevated (compared to baseline) at 96 hours (-2/+12 hours) after the start of the infusion, the participant must be discontinued from the study and biochemistry followed until resolution. The Sponsor must be notified immediately.

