In general, if a participant experiences a Grade 1 or Grade 2 haematological or non-haematological toxicity, no dose modification is required. If a participant experiences a Grade 3 or Grade 4 toxicity, not attributable to the disease or disease-related processes under investigation, dosing might be interrupted and/or the dose reduced (see [Table 12](#) for acalabrutinib reduction options and [Table 13](#) for recommended dose modifications for AZD4573 and acalabrutinib) and supportive therapy administered as required. If the toxicity resolves or reverts to CTCAE Grade ≤ 2 within 21 days and the participant was showing clinical benefit, treatment with study treatment(s) may be restarted.

If the toxicity does not resolve to CTCAE Grade ≤ 2 within 21 days, then the participant should be withdrawn from the study and observed until resolution of the toxicity. Maximal drug interruption allowed for related toxicity for both AZD4573 and acalabrutinib is ≤ 21 consecutive days.

Table 13 Recommended Dose Modifications for AZD4573 and Acalabrutinib

Event ^a	Occurrence	Action with AZD4573	Action with Acalabrutinib
Tumour Lysis Syndrome (TLS) – Howard Modification of Cairo-Bishop Criteria			
Changes in uric acid, potassium, phosphorus, creatinine or calcium, or symptoms suggestive of clinically significant TLS, in the Investigator's judgement	Any	For any abnormal changes present before dosing, initiate supportive therapy and hold drug for up to 7 days. If not resolved, reduce by 1 dose level.	Withhold acalabrutinib until resolved, resume dosing at the same dose level upon resolution.
		For events of Grade 1 or 2 TLS, resume at same dose level upon resolution.	For events of Grade 1 or 2 TLS, resume at same dose level upon resolution.
		For 1st occurrence of Grade 3 TLS resume at the same dose upon resolution to Grade 1.	For 1st occurrence of Grade 3 TLS resume at the same dose upon resolution.

Table 13 Recommended Dose Modifications for AZD4573 and Acalabrutinib

Event ^a	Occurrence	Action with AZD4573	Action with Acalabrutinib

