Event ^a	Action	
	AZD4573	Acalabrutinib
Isolated^b elevations in ALT, AST, or bilirubin		
Grade 1 Isolated ALT/AST \leq 3 \times ULN or Isolated Bilirubin \leq 1.5 \times ULN	Maintain current dose level. Monitor ALT, AST, ALP, and bilirubin at least 1x per week.	Maintain current dose level and schedule. Monitor ALT, AST, ALP, and bilirubin at least 1x per week.

Event ^a	Action	
	AZD4573	Acalabrutinib
Grade 2 Isolated ALT/AST > 3 to $\leq 5 \times$ ULN or Isolated Bilirubin > 1.5- $\leq 3 \times$ ULN	After 7 days if hepatic enzymes resolve to Grade ≤ 1 , rechallenge at same dose level.	Withhold or continue acalabrutinib (at Investigator discretion, after discussion with the Medical Monitor). To prevent disease progression, monitor disease parameters closely. Monitor ALT, AST, ALP, and bilirubin at least 1x per week. After 7 days if hepatic enzymes appear to be improving and acalabrutinib was withheld, restart acalabrutinib at current dose level.
Grade 3 Isolated ALT/AST > 5-20 \times ULN	If recovered to Grade ≤ 1 within 7 days, allow rechallenge at same dose level. If not recovered to baseline level within 7 days, discontinue AZD4573.	Withhold or continue acalabrutinib (at Investigator discretion, after discussion with the Medical Monitor). To prevent disease progression, monitor disease parameters closely.
Grade 3 Isolated Bilirubin > 3-10 \times ULN	If recovered to baseline level within 96 hours (-2/+12 hours) of the start of the infusion allow rechallenge at same dose level. If not, discontinue AZD4573	Monitor ALT, AST, ALP, and bilirubin at least 1x per week. After 7 days if hepatic enzymes appear to be improving and acalabrutinib was withheld, restart acalabrutinib with 1 level dose reduction or discontinue.
Grade 4^c Isolated ALT > 20 \times ULN or Isolated Bilirubin > 10 \times ULN	Discontinue AZD4573.	Discontinue acalabrutinib.
Grade 4 Isolated elevation ($\geq 20 \times$ ULN) in AST without concomitant elevation in ALT $\geq 20 \times$ ULN or concomitant elevation in TBL $\geq 2 \times$ ULN that fails to return to baseline level within 7 days from start of dosing	Discontinue AZD4573.	Discontinue acalabrutinib.

Event ^a	Action	
	AZD4573	Acalabrutinib

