Grade 4^c Isolated AST elevation $\geq 20 \times$ ULN without concomitant elevation in ALT $\geq 20 \times$ ULN or TBL $\geq 2 \times$ ULN	1st occurrence If recovered to Grade ≤ 1 or baseline level within 7 days of the start of the infusion allow rechallenge at same dose level 2nd occurrence If recovered to Grade ≤ 1 or baseline level within 7 days of the start of the infusion allow rechallenge with 1 dose level reduction 3rd occurrence Discontinue AZD4573	Withhold or continue acalabrutinib (at Investigator discretion, after discussion with the Medical Monitor). To prevent disease progression, monitor disease parameters closely. Monitor ALT, AST, ALP, and bilirubin at least 1x per week. After 7 days if hepatic enzymes appear to be improving and acalabrutinib was withheld, restart acalabrutinib at current dose level at the 1st occurrence and with 1 level dose reduction at the 2nd occurrence . Discontinue acalabrutinib at the 3rd occurrence .
Concurrent elevations in ALT, AST, or bilirubin (Please also refer to Appendix E for actions to be taken in the event of PHL)		
ALT or AST $\geq 3 \times$ ULN with TBL $\geq 2 \times$ ULN (Potential Hy's Law) AND INR $\geq 1.5 \times$ ULN (or $\geq 1.5 \times$ baseline if elevated at baseline) of any duration	Discontinue AZD4573.	Discontinue acalabrutinib.
ALT or AST $\geq 3 \times$ ULN with the appearance of fatigue, nausea, vomiting, right upper quadrant pain or tenderness, fever, rash, and/or eosinophilia $> 5\%$	Discontinue AZD4573.	Discontinue acalabrutinib.
ALT or AST $\geq 3 \times$ ULN and TBL $\geq 2 \times$ ULN where TBL does not return to baseline level within 96 hours (-2/+12 hours) from start of dose and/or AST or ALT do not return to baseline level within 7 days from start of dose	Discontinue AZD4573.	Discontinue acalabrutinib.

Event ^a	Action	
	AZD4573	Acalabrutinib
Grade 3 elevation ($\geq 5 \times$ ULN) in ALT or AST with TBL elevation above baseline level or ULN, but $< 2 \times$ ULN that do not return to baseline level within 7 days	Discontinue AZD4573.	Discontinue acalabrutinib.

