ALT and AST $\geq 3 \times$ ULN with concomitant TBL $\geq 2 \times$ ULN, NO increase in INR $\geq 1.5 \times$ ULN (or $1.5 \times$ baseline), and NO fatigue, nausea, vomiting, right upper quadrant pain or tenderness, fever, rash, and/or eosinophilia $> 5\%$	If recovered to Grade ≤ 1 or baseline level within 96 (-2/+12) hours, rechallenge at same dose level ^c	Withhold acalabrutinib until recovered. Once recovered, restart acalabrutinib at same dose.

^a Adverse reactions are graded using National Cancer Institute CTCAE version 5.0. All grades refer to CTCAE grading except for TLS, which uses the Howard modification of Cairo-Bishop criteria (Howard et al 2011).

^b Elevations in ALT or AST are considered isolated if bilirubin remains below Grade 1, and elevations in bilirubin are considered isolated if ALT and AST remain below Grade 1.

^c Participants who are considered for rechallenge in the event of Grade 4 transaminase increases or PHL must discuss possible risk of hepatotoxicity with the treating physician, who will document this discussion and participant agreement for continued treatment in the medical records.

Note: Adequate supportive therapy as per institutional guidelines should be given for all toxicities.

Abbreviations: ALP = alkaline phosphatase; ALT = alanine aminotransferase; AST = aspartate aminotransferase; CTCAE = Common Terminology Criteria for Adverse Events; INR = international normalised ratio; PHL = Potential Hy's Law; TBL = total bilirubin; ULN = upper limit of normal.

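### Table 14 gives both a rechallenge and a stop instruction when bilirubin is at Grade 1 but above baseline at 96 hours, and ties the Grade 4 ALT stop to bilirubin being below Grade 1

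*Protocol*

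**What the plan says.** Table 14 (Section 15.12, Module 1) treats isolated and concurrent liver abnormalities separately.

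- **Isolated Grade 4.** For isolated ALT > 20 × ULN or isolated bilirubin > 10 × ULN, AZD4573 is discontinued and the acalabrutinib entry is "Discontinue acalabrutinib". No recovery condition is attached. Footnote b limits the row: "Elevations in ALT or AST are considered isolated if bilirubin remains below Grade 1", and bilirubin counts as isolated only if both transaminases are below Grade 1.
- **Concurrent, slow recovery.** For ALT or AST ≥ 3 × ULN with TBL ≥ 2 × ULN, both drugs stop "where TBL does not return to baseline level within 96 hours", or where ALT or AST is not back to baseline within 7 days.
- **Concurrent, last row.** For ALT and AST ≥ 3 × ULN with TBL ≥ 2 × ULN, no INR rise and none of the listed symptoms, recovery to Grade 1 or below "or baseline level within 96 (-2/+12) hours, rechallenge at same dose level" is the AZD4573 rule. For acalabrutinib: "Once recovered, restart acalabrutinib at same dose". The row sets no ceiling on ALT or bilirubin.

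Section 15.2 separately requires discontinuation in potential Hy's Law (PHL) cases "if bilirubin remains elevated (compared to baseline) at 96 hours" after the start of infusion. Section 15.3 counts ALT ≥ 20 × ULN as a DLT at any duration and any bilirubin.

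**The concern.** Transaminase rises, alone and together with bilirubin, are listed in Section 2.3.1 as important identified risks of AZD4573, and this table guides who is dosed again.

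(a) For a qualifying PHL event, the last row judges recovery by Grade 1 or baseline, while the slow-recovery row and Section 15.2 judge TBL by baseline alone. Between those two thresholds the protocol gives opposite instructions for the same participant. Two sites could act differently and each point to a rule.

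(b) The unconditional stop for Grade 4 ALT falls away once bilirubin is also raised. Of two participants with the same ALT, the one with normal bilirubin is to be stopped, while the one with TBL ≥ 2 × ULN and rapid recovery may be rechallenged at full dose. The supplied text does not explain why the isolated elevation is handled more strictly.

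**Working it through.** The protocol states no figure to reproduce. The check applies the rules to defined cases. Case values are illustrative, in multiples of ULN.

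**1. The conflict in (a).** Assume baseline TBL 0.7, peak 2.5, 96-hour value 1.3; ALT and AST ≥ 3 at peak and recovered to baseline; normal INR; no listed symptoms.

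- Entry to the concurrent rows: 2.5 ≥ 2, met.
- Last row: Table 14 puts Grade 1 bilirubin at ≤ 1.5. Since 1.3 ≤ 1.5, the participant has recovered and may be rechallenged.
- Slow-recovery row: 1.3 > 0.7, so TBL is not at baseline and both drugs stop.
- Section 15.2: bilirubin is above baseline at 96 hours, so discontinue.

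The overlap covers any 96-hour TBL above baseline and up to 1.5. With baseline 0.7, that band is 1.5 − 0.7 = 0.8 × ULN wide. Table 2 (Section 5.1) admits participants without Gilbert's syndrome at ≤ 1.5, so some overlap exists for any such baseline below that limit. It does not need Grade 4 ALT. A similar conflict arises if ALT or AST is at Grade 1 at 96 hours but not at baseline by day 7.

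**2. The asymmetry in (b).** Take ALT 25 and AST 10 throughout.

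| TBL | INR | Symptoms | Recovery | Row(s) met | Action |
|---|---|---|---|---|---|
| 0.8 | normal | none | fast | isolated Grade 4 ALT | stop both |
| 2.5 | normal | none | all at baseline by 96 h | last concurrent row only | same-dose rechallenge |
| 2.5 | 1.6 | none | fast | INR row | stop both |
| 2.5 | normal | present | fast | symptom row | stop both |
| 2.5 | normal | none | slow | slow-recovery row | stop both |
| 2.5 | normal | none | TBL at Grade 1, above baseline, at 96 h | slow-recovery and last rows | conflict, as in (a) |

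Only the second line shows the asymmetry.

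**3. How narrow (b) is.** Table 14 puts Grade 1 ALT at ≤ 3 × ULN. From > 20 to ≤ 3 is a fall of at least 1 − 3/20 = 85%, or log2(20/3) = 2.74 halvings. The longest window is 96 + 12 = 108 hours, so ALT must halve about every 108/2.74 ≈ 39 hours or faster, even if it peaked at the start of infusion. It must then reach baseline by day 7. AST must have been ≥ 3 × ULN, INR normal, and nausea, vomiting, fatigue, fever and the other listed signs absent. Section 17.1.10.3 reports nausea and vomiting in about half of those dosed with AZD4573.

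**The case against.** On (a), Section 15.2 is mandatory and Table 14 is titled as recommended, so a careful investigator would stop. That indicates which way to correct the row but does not remove the conflict: the slow-recovery and last rows sit in the same table, and Section 15.12.1 item 3 refers back to that table's time limits.

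On (b), a reader might infer that the participant is redosed automatically. The protocol does not support that. Section 6.12 requires Medical Monitor discussion before dosing resumes after a possibly related significant reaction or DLT. PHL cases are SAEs (Section 8.2.6) under joint review (Section 17.1.10.9). Footnote c and Section 15.12.1 add a documented risk discussion and continued consent. The isolated Grade 4 row itself carries footnote c, which concerns rechallenge, so its intent is less clear than its action column. All of this stands and reduces (b) to an asymmetry in the written rule.

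A reader might also infer a contradiction with Section 15.3. There is none, since a DLT does not by itself force discontinuation. The comparison shows only that the DLT rule ignores bilirubin where the stop rule depends on it.

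A third tempting inference is a gap for Grade 4 ALT with TBL between ULN and 2 × ULN, where the only concurrent row specific to that bilirubin range covers events "that do not return to baseline level within 7 days". General rules still apply: under Section 15.12 "dosing might be interrupted and/or the dose reduced", and Sections 6.12, 15.12.1 and 17.1.10 also govern. That is missing detail, not an error.

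Finally, Section 17.1.10.9 gives a reason for tolerating rapidly reversing combined rises: they have so far left no lasting harm. That supports the lenient row but does not explain the stricter isolated one.

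**Conclusion.** Point (a) stands as a direct conflict: two rows of one table give opposite actions for the same PHL event, and Section 15.2 sides with the stop. Point (b) stands as an unexplained asymmetry: the participant may be rechallenged after case-level review.

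The size is minor to moderate. The supplied text gives no frequency for either situation. Case (b) is narrow, recruitment has stopped (Section 4.1), and only participants still on treatment are affected. Their number is not given, and Sections 6.13 and 15.7 also direct them to the Investigator's Brochure.

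The conclusion assumes that Table 14's own grade limits apply and that baseline means the participant's own pre-treatment value. Appendix E, cited in the table for PHL, was not supplied and could restrict (b). It would not remove the opposing entries behind (a) from Table 14.

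**What to change.** 1. Reword the recovery test in the last concurrent row: TBL back to baseline within 96 (−2/+12) hours, and ALT and AST back to baseline within 7 days. This matches the slow-recovery row and Section 15.2 and keeps the separate time limits for bilirubin and transaminases.
2. Have the sponsor's hepatic experts choose one direction for Grade 4 values. Either apply the ALT > 20 × ULN and bilirubin > 10 × ULN stops whatever the other marker shows, and cap the last row at ALT ≤ 20 × ULN and TBL ≤ 10 × ULN; or, if rechallenge is intended, make the isolated row no stricter than the combined one. Check Appendix E first, and keep footnote c on the Grade 4 row only if that row allows rechallenge.

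The cost is a wording change to two rows of one table in an amendment. All markers are already measured, and no participants, visits or tests are added.

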15.12.1 Retreatment Criteria

Retreatment is defined as the first dose of study drug after a significant period of intentional pause in study drug treatment (other than missed doses, eg, study treatment put on hold until resolution of COVID-19).

Retreatment criteria (criteria to be met before participant restarts study drug infusions [and capsules, as applicable]):

All participants:

- 1 Participant has recovered from all treatment-related non-haematological toxicity to CTCAE Grade ≤ 2 .
- 2 Recovery of neutrophils $\geq 1000/\mu\text{L}$ and platelets $\geq 50,000/\mu\text{L}$.
- 3 Participant has recovered from all hepatic toxicity events within the timeframes described in Table 14 above. If biochemical changes in transaminase(s) and total bilirubin are consistent with the definition of HL, the participant may continue to receive study drug

only if all abnormalities have resolved within the timeframes specified in [Table 14](#) above, there are no symptoms of liver injury and INR has not increased above $1.5 \times$ ULN (or $1.5 \times$ baseline). In these circumstances the participant must be made aware of the unknown potential for liver damage with continued exposure to AZD4573 prior to retreatment. Documentation of continued consent is required.

- 4 Recovery of uric acid to $<$ ULN.
- 5 Recovery of changes in uric acid, potassium, phosphorus, creatinine or calcium, or symptoms suggestive of TLS as defined in [Table 13](#).
- 6 In case of any new deterioration in laboratory values, not fulfilling eligibility criteria and deemed as clinically significant by the Investigator, the Medical Monitor must be contacted to discuss whether AZD4573 dosing can be continued.

15.13 Intervention After the End of the Study

No intervention is planned after the end of the study. However, provisions will be in place for patients still enrolled at the end of the trial to continue to receive study intervention if, in the opinion of the Investigator, they are continuing to receive benefit from treatment.

16 DISCONTINUATION OF STUDY INTERVENTION AND PARTICIPANT DISCONTINUATION/WITHDRAWAL – MODULE 1

16.1 Discontinuation of Study Intervention

See the SoA for data to be collected at the time of intervention discontinuation and follow-up and for any further evaluations that need to be completed.

Please refer to Section [7.1](#) for information on discontinuation of study intervention.

16.1.1 Temporary Discontinuation

Refer to Section [15.12](#) for information on temporary discontinuation and restarting of study intervention.

16.1.2 Rechallenge

Refer to Section [15.12](#) for information on rechallenge with study intervention.

16.2 Participant Withdrawal from the Study

Please refer to Section [7.2](#) for information on participant withdrawal from the study.

16.3 Procedures for Handling Participants Incorrectly Initiated on AZD4573 or Combination Therapy

Please refer to Section [7.3](#) for information on procedures for handling participants incorrectly initiated on AZD4573 or combination therapy.

16.4 Lost to Follow-up

A participant will be considered lost to follow-up if he or she repeatedly fails to return for scheduled visits and is unable to be contacted by the study site.

Please refer to Section [7.4](#) for actions to be taken if a participant fails to return to the clinic for a required study visit.

For handling of discontinuation of specific sites or of the study as a whole please refer to Appendix [A 9](#).

17 STUDY ASSESSMENTS AND PROCEDURES – MODULE 1

- Study procedures and their timing are summarised in the SoA (Section 10.2). Protocol waivers or exemptions are not allowed.
- Immediate safety concerns should be discussed with the Medical Monitor immediately upon occurrence or awareness to determine if the participant should continue or discontinue study intervention.
- Adherence to the study design requirements, including those specified in the SoA, is essential and required for study conduct.
- All screening evaluations must be completed and reviewed to confirm that potential participants meet all eligibility criteria. The Investigator will maintain a screening log to record details of all participants screened and to confirm eligibility or record reasons for screening failure, as applicable.
- Procedures conducted as part of the participant's routine clinical management (eg, blood count) and obtained before signing of the ICF may be utilised for screening or baseline purposes provided the procedures met the protocol-specified criteria and were performed within the time frame defined in the SoA.
- The amount of blood collected from each participant for the scheduled assessments, is not anticipated to exceed 440 mL in Cycle 1 (cycle duration 5 weeks), 135 mL in Cycle 2 (cycle duration 3 weeks) and 80 mL in each subsequent cycle (cycle duration 3 weeks). If a participant experiences TLS, maximum 30 mL extra blood will be collected per cycle (5 weeks) for safety reasons. **CCI**

Repeat or unscheduled samples may be taken for safety reasons or for technical issues with the samples.

17.1 Safety Assessments

17.1.1 Enrolment and Screening

Each potential participant approved for screening is assigned a unique participant enrolment number. If a participant withdraws from the study, then the enrolment number cannot be reused.

Demographic data and other characteristics will be recorded and will include date of birth, race and ethnicity, and alcohol use.

A standard medical, medication and surgical history will be obtained with review of the selection criteria with the participant. Concurrent medical signs and symptoms must be documented to establish baseline severities. Previous and concomitant treatments (coded

according to the World Health Organization Drug Dictionary [WHODRUG]) will be collected for each participant. A disease history, including the date of initial diagnosis, staging within 30 days of first dose of AZD4573, prognostic indices/disease profiling for DLBCL (derived from local laboratory results) and list of all prior anti-cancer treatments, and responses and DoR to these treatments, will also be recorded.

Each participant will undergo screening (see Section 10.2) during the 30 days before admission to confirm eligibility (see Sections 14.1 and 14.2).

